monotherapy studies of INCB050465 in NHL. Once a treatment regimen is selected, the non-selected treatment regimen will be closed to further enrollment. Subjects receiving the non-selected treatment regimen may switch to the selected treatment regimen or remain on their current treatment regimen, provided the subject has not met study-treatment withdrawal criteria and there are no safety concerns for their current treatment regimen. There will be no re-baselining for subjects who switch treatment regimens and all subjects will continue to follow the same assessment schedule.

NOTE: The primary, secondary, [REDACTED] objectives and endpoints described in Section 2 are applicable for both cohorts; however, the cohorts will be analyzed separately, when applicable, as detailed in Section 9.

[figure not shown]
Subjects will receive treatment until disease progression, death, unacceptable toxicity, or consent withdrawal.

Subjects will be monitored for safety and efficacy periodically until disease progression, death, unacceptable toxicity, or withdrawal of informed consent. An IDMC will review safety data periodically as stated in the IDMC charter. Subjects will be evaluated for ORR by an IRC and followed for DOR, PFS, and OS.

An interim futility analysis is planned for Cohort 2 when 30 subjects have been treated and have been evaluated for response or have permanently discontinued study treatment because of disease progression, withdrawal of consent, or death. Cohort 2 will be terminated for futility if ≤ 10 of the 30 subjects responded (ie, CR or PR) based on assessments provided by the IRC. A timely assessment of response will be performed to avoid the risk of overenrollment.

After treatment discontinuation, subjects will be followed for safety and survival. Subjects who have discontinued study treatment due to reasons other than disease progression will be followed for either radiologic disease progression, the start of a new anticancer therapy, or death, whichever comes first. It is expected that the final analysis will occur no later than 2 years after the first dose of INCB050465 is administered to the last subject treated.

Figure 1: Study Design of INCB 50465-204

BTKi = Bruton's tyrosine kinase inhibitor; EOT = end of treatment; MZL = marginal zone lymphoma; QD = once daily

^a A futility analysis will be performed for Cohort 2 when the first 30 patients have been treated and evaluated for response (see Section 9.6).

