5.5.1. Criteria for Study Treatment Discontinuation

Subjects **must** be withdrawn from study treatment for any 1 of following reasons:

- The subject has experienced an unacceptable toxicity defined as follows:
 - Occurrence of an AE that is related to study treatment that, in the judgment of the investigator or the sponsor's medical monitor, compromises the subject's ability to continue study-specific procedures or is considered to not be in the subject's best interest.
 - Persistent AE requiring a delay of therapy for more than 2 weeks (14 days) unless a greater delay has been approved by the sponsor.
- The subject is unable to tolerate study treatment.
- The subject has an objective radiographic tumor response of PD.
- Further participation would be injurious to the subject's health or well-being, in the investigator's medical judgment.
- The subject becomes pregnant.
- Informed consent is withdrawn.
Note: Consent withdrawn means that the subject can no longer be followed. Subjects may choose to discontinue study treatment and remain in the study to be followed for disease progression and survival per the schedule of assessments.
- The study is terminated by the sponsor.
- The study is terminated by the local health authority, IRB, or IEC.

A subject **may** be discontinued from study treatment in the following situations:

- If a subject is noncompliant with study procedures or study treatment administration in the investigator's opinion, then the sponsor should be consulted for instruction on handling the subject.

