### **5.2. Treatment Groups**

This is a Phase 2, open-label study. All analyses will be conducted independently for Cohort 1 and Cohort 2, and there will not be multiplicity adjustment between the cohorts. Within each cohort, there will not be any statistical comparison between the treatment groups.

For the purpose of analysis, the 20 mg QW dosing period in Treatment A and the 2.5 mg QD dosing period in Treatment B are considered maintenance dosing periods. Within each cohort, data will be presented in summary tables by actual received treatment regimen and combined, with an exception for participants who cross over to the selected treatment regimen after the start of the maintenance dosing period.

For participants who cross over from the initially assigned treatment regimen to the selected treatment regimen, if the crossover happens before/on the start of the maintenance dosing period, then the participant will be summarized, according to the actual received treatment, in the selected treatment regimen; otherwise, the participant will be summarized in:

- A separate treatment regimen (ie, Crossover) for the safety summaries during the maintenance dosing period (eg. summaries of TEAEs and exposure).
- The initially assigned treatment regimen for all other summaries.

Per Protocol Amendment (Version) 3, Cohort 1 was closed to further enrollment. If the number of participants who have enrolled in Cohort 1 is relatively few, summary tables will be replaced with listings.

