## 6.4. Exposure

For participants in the safety population, exposure to INCB050465 will be summarized descriptively as the following:

- **Duration of treatment (days):** Date of last dose – date of first dose + 1.
- **Duration of treatment during the initial QD dosing period (days):** Date of last dose during the initial QD dosing period – date of first dose + 1.
- **Duration of treatment during the maintenance dosing period (days):** Date of last dose – date of first dose during the maintenance dosing period + 1. Crossover participants who switched to the selected treatment regimen after the start of the maintenance dosing period will be summarized in a separate group (ie, Crossover).
- **Average reported daily dose during the initial QD dosing period (mg/day):** total reported dose taken during the initial QD dosing period (mg) / duration of treatment during the initial QD dosing period (days).
- **Average reported daily dose during the maintenance dosing period (mg/day):** total reported dose taken during the maintenance dosing period (mg) / duration of treatment during the maintenance dosing period (days). Crossover participants who switched to the selected treatment regimen after the start of the maintenance dosing period will be summarized in a separate group (ie, Crossover).
- **Dose modifications:** Number of participants who had dose reduction and interruption will be summarized. The number of dose reductions and the number of interruptions for each participant will be summarized.

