#### **7.3.1. Best Overall Response and Objective Response Rate**

For responses as determined by IRC, the best overall response for each participant will be provided by the clinical reviewer. A participant is considered an objective responder if they have a best overall response of CR or PR.

The ORR is the proportion of objective responders. Participants who do not have sufficient baseline or on-study response assessment information to be adequately assessed for response status will be included in the denominators in the calculation of ORR.

Best overall response as determined by IRC will be summarized descriptively. The ORR as determined by IRC with 95% CIs will be calculated. Confidence intervals will be calculated based on the exact method for binomial distributions.

Because participants who switched to the selected treatment regimen after starting the maintenance dose received a mixture of the non-selected and selected maintenance regimens and could confound the efficacy evaluation of the non-selected treatment regimen, a sensitivity analysis of ORR as determined by IRC will be provided to summarize these crossover participants as a separate treatment regimen. In addition, the number of participants who achieved best overall response as determined by IRC after the time of crossover along with the best overall response data will be presented under this separate treatment regimen. The analyses described above will be summarized for all participants and participants who have at least 2 prior therapies in the FAS.

When applicable, sensitivity analysis of ORR as determined by an IRC may be provided excluding participants that do not have evaluable radiological images at baseline per the IRC.

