### **7.4.2. Complete Response Rate**

Complete response rate is the percentage of participants with a best overall response of CR as defined by revised response criteria for lymphomas ([Cheson et al 2014](#)). For responses as determined by IRC, the best overall response for each participant will be provided by the clinical reviewer. Participants who do not have sufficient baseline or on-study response assessment information to be adequately assessed for response status will be included in the denominators in the calculation of CRR.

The CRR as determined by IRC will be estimated with 95% CIs for all participants and participants who have at least 2 prior therapies in the FAS. Confidence intervals will be calculated based on the exact method for binomial distributions.

A sensitivity analysis of CRR will be provided to summarize participants who switched to the selected treatment regimen after starting the maintenance dose as a separate treatment regimen.

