- Summary of time to onset of selected TEAEs of special interest: life-table method
- Summary of longest duration of selected TEAEs of special interest

The following supporting summaries will be produced for TEAEs during the INCB050465 initial QD dosing period and the maintenance dosing period by MedDRA term. For the supporting summaries during the maintenance dosing period, participants who cross over to the selected treatment regimen after the start of the maintenance dosing period will be summarized in a separate group (ie, Crossover).

- Summary of TEAEs by PT in decreasing order of frequency
- Summary of TEAEs by PT and maximum severity in decreasing order of frequency
- Summary of Grade 3 or higher TEAEs by PT in decreasing order of frequency
- Summary of serious TEAEs by PT in descending order of frequency
- Summary of TEAEs with a fatal outcome by SOC and PT
- Summary of TEAEs leading to discontinuation of INCB050465 by SOC and PT

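### The Crossover group is selected on having stayed on regimen A and carries A's pre-switch responses, exposure and TEAEs; add displays cut at the switch (minor)

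*SAP*

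**What the plan says.** **Who can switch.** Protocol Section 4.1 lets participants on the non-selected regimen move to the selected one "provided the subject has not met study-treatment withdrawal criteria". Protocol Section 5.5.1 lists the reasons that force withdrawal, among them "The subject has an objective radiographic tumor response of PD" and unacceptable toxicity. SAP Section 11.2 (Amendment 1) records that B was selected, so switchers come from A.

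**Response.** In SAP Section 7.3.1 "a sensitivity analysis of ORR as determined by IRC will be provided to summarize these crossover participants as a separate treatment regimen". For CRR, Section 7.4.2 will "summarize participants who switched to the selected treatment regimen after starting the maintenance dose as a separate treatment regimen". Both use best overall response, which is not cut at the switch. In Appendix A, Table 2.4.1 is the split and Table 2.4.3 covers the switchers' best response.

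**Safety.** SAP Section 5.2 places participants who switch after starting maintenance in "A separate treatment regimen (ie, Crossover) for the safety summaries during the maintenance dosing period" and in "The initially assigned treatment regimen for all other summaries". Section 6.4 runs maintenance exposure from the first maintenance dose to the last dose, and "Crossover participants who switched to the selected treatment regimen after the start of the maintenance dosing period will be summarized in a separate group". Section 9.2.3 says of the supporting TEAE summaries that "participants who cross over to the selected treatment regimen after the start of the maintenance dosing period will be summarized in a separate group". A's weekly dosing period counts as maintenance, so pre-switch time on A falls inside it.

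**Duration endpoints.** DOR and PFS (Sections 7.4.1 and 7.4.3) each have a sensitivity analysis that drops assessments after crossover. The DOR version counts a switcher as a responder only if response came by the crossover date.

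**The concern.** Membership of Crossover depends on a post-baseline event, namely being on treatment when B was selected. Earlier progressors and discontinuers on A cannot enter it and stay in residual A. If non-responders leave treatment sooner than responders, the two rows differ in ORR even when the regimens are identical, and Crossover also shows responses reached on A. The SAP gives the split because switchers could confound evaluation of the non-selected regimen. Taking them out replaces that mixture with a selected remainder.

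In the maintenance safety tables, a switcher's weekly-dosing time and events on A appear under Crossover. These displays include TEAEs leading to discontinuation, and Protocol Section 1.5 says the two regimens were proposed to see whether AEs leading to withdrawal become less frequent. A reader looking there for A's tolerability would see a selected subset.

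Appendix A plans no ORR or CRR with a confidence interval that keeps these switchers in A and stops counting at the switch.

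**Working it through.** The plan gives no figure for this effect. The number on A, selection date, uptake, dropout and event rates are not stated, so every size below is conditional. The regimens are identical throughout, so any gap is an artefact.

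**1. ORR, closed form.** Assumed: true ORR 60%; responses reached before selection; 18-month uniform accrual with selection at month 20, so time on study at selection is uniform on 2 to 20 months; responders leave treatment with median 24 months; AE stops at 0.30 per year in everyone; uptake u among those still on treatment.

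Monthly hazard k = ln2/median + 0.30/12. Share still on treatment at selection: S = (e^(−2k) − e^(−20k)) / (18k).

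- Responders: k = 0.0539, S_R = 0.575.
- Non-responders: median 6 gives k = 0.1405, S_N = 0.275; median 12 gives k = 0.0828, S_N = 0.441; median 24 gives S_N = 0.575.

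Crossover ORR = 0.6·S_R / (0.6·S_R + 0.4·S_N). Residual-A ORR = 0.6(1 − u·S_R) / [0.6(1 − u·S_R) + 0.4(1 − u·S_N)].

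| Non-responder median (months) | Uptake | Crossover | Residual A | Gap (points) |
|---|---|---|---|---|
| 6 | 50% | 75.8% | 55.3% | 20.5 |
| 6 | 100% | 75.8% | 46.8% | 29.0 |
| 12 | 50% | 66.2% | 57.8% | 8.4 |
| 12 | 100% | 66.2% | 53.3% | 12.9 |
| 24 | any | 60.0% | 60.0% | 0 |

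**2. ORR, simulation.** This uses the same inputs with 30 on A, cutoff at month 32, and 15% of responses at weeks 16–36 (the rest at week 8).

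- Medians 6–12: residual A 44–57%, Crossover 68–77%, gap 11–32 points.
- Median 24: 58–59% against 62%, gap 2–4 points.
- All of A, counting response on or before the switch: 58–59% throughout.
- Wider grid (later selection, longer follow-up, shorter responder median, more late responses): gap from −2 to 36 points.

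**3. Crude TEAE incidence in maintenance.** Assume a true rate of 20 per 100 patient-years everywhere. Simulated mean maintenance exposure is 4.6–10.6 months in residual A and 15.4–16.6 in Crossover, of which 7.3–7.8 months is on A. Incidence ≈ 1 − e^(−0.20·T/12):

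- Residual A: T = 4.6 gives 7.4%; T = 10.6 gives 16.2%.
- Crossover: T = 15.4 gives 22.6%; T = 16.6 gives 24.2%.

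The simulation gives 7–16% against 22–24%, and 47–56% of Crossover's first maintenance TEAEs fall before the switch. Residual A looks safer only because it was observed for less time.

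**4. AE discontinuation in maintenance.** Assume 35% stop for an AE by 12 months, so h = −ln(0.65)/12 = 0.0359 per month, over 18 months of maintenance. A fraction q of those still on treatment switches at month s.

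- All A: 1 − e^(−18h) = 47.6%.
- Crossover: 1 − e^(−h(18−s)) = 41.6%, 35.0%, 27.6% for s = 3, 6, 9.
- Residual A: (0.476 − c·Crossover)/(1 − c), with c = q·e^(−hs). For s = 6, q = 0.5: c = 0.403 and (0.476 − 0.403 × 0.350)/0.597 = 56%. Over s = 3–9 and q = 0.5–0.8: 52–75%.

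Here residual A looks worse. The true rate is 12h = 0.43 per patient-year. Crossover shows 0.20–0.34 when pre-switch time is counted, and 0.43 when counting starts at the switch.

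**The case against.** The strongest reply is that Crossover is a labelled mixture. The SAP itself says these participants received both maintenance regimens, so time on A inside the group follows from its definition. The ORR and CRR splits came in with Amendment 2, written to comply with responses to FDA comments. Table shells are in a separate document, so explanatory footnotes may already exist.

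Much of the remedy is also planned. By-regimen ORR and CRR with full follow-up keep these switchers in A. Table 2.4.5 will carry the on-or-before responder count, and Listing 2.6.14 gives best response with crossover participants censored. What is missing for ORR is a division by a known denominator and an exact interval. That interval is wide: 18/30 gives 40.6–77.3%, against a 1–2 point change in A's ORR in the assumed base case. For CRR the gain is smaller still. With true CRR 10% and half of CRs late, full-follow-up A gives 8.0–8.1%, the on-or-before row 6.3–7.2% and residual A 5.3–7.6%. Finally, Protocol Section 5.4.4 says most immune-related events come after the first 9 weeks, so a cut at the switch may assign late effects of A to the post-switch period.

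All of this limits the importance of the point and shapes the fix. It does not remove the selection or the placement of A's time and events. The planned post-crossover response count does not fill the gap either: a PR on A that deepens to CR after the switch counts as post-crossover, although that participant was already a responder.

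**Conclusion.** The point holds as a minor one, confined to the residual-A and Crossover columns of sensitivity and supporting displays. Those rows are selected on remaining on A, and neither describes A.

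The size rests on assumption. With identical regimens the ORR gap runs from about none to about 30 points, depending mainly on how much sooner non-responders leave treatment. For safety the direction depends on the measure: crude TEAE incidence is lower in residual A, AE discontinuation higher.

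Three stronger readings are tempting, and the documents do not support them:

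- **That the headline ORR is biased.** Protocol Section 9.4 pools A and B for the primary and secondary efficacy analyses. The main by-regimen tables, overall-period TEAE tables and column B are also unaffected, and SAP Section 3.2 plans no comparison of regimens.
- **That the split will make A look worse by a known amount.** No switch or dropout data are given, the ORR gap can be nil, and crude TEAE incidence moves the other way.
- **That unequal follow-up or post-switch response is ignored altogether.** DOR and PFS have crossover-censored analyses, and time to onset of events of special interest uses censoring and life tables.

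**What to change.** Make additions only; keep every planned display.

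1. **Response (SAP 7.3.1, 7.4.2, Appendix A).** Add one table of ORR per IRC with exact CIs, with CRR alongside mainly for attribution, over the FAS under the Section 5.2 grouping. Participants who switched before or on the start of maintenance stay in the selected regimen with no cut. Those who switched after starting maintenance stay in the initially assigned regimen and count as responders only if IRC response was reached on or before the crossover date. This is the Section 7.4.1 rule, so the responder count should match Table 2.4.5. Keep Tables 2.4.1–2.4.4 and the full-follow-up by-regimen ORR and CRR. Footnote that Crossover is selected on remaining on treatment and includes responses reached before the switch.

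2. **Safety (SAP 5.2, 6.4, 9.2.3).** Keep the Crossover maintenance summaries. For those who switched after starting maintenance, add exposure and TEAEs split at the switch: pre-switch under the assigned regimen, post-switch shown separately. Give exposure-adjusted incidence beside n (%). Note that post-switch events may include late-onset events from A, and that a constant rate may not hold for immune-related events.

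**Cost.** SAP wording, one table, and reprogramming to split exposure and AE windows. No new data are needed, since the IRC already supplies timepoint responses and the initial-response date. A's on-or-before ORR is 1–2 points lower in the assumed base case, and up to about 8 if 30% of responses are spread over weeks 16–96. Late CRs are also lost, so the full-follow-up rows must stay beside the new ones.

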#### **7.3.2. Subgroup Analyses for Objective Response Rate**

Subgroups will be formed based on the following participant characteristics and baseline variables:

- Age: < 65 years,  $\geq$  65 years
- Gender: male, female
- Race: White, Others
- Geographic region: Europe, North America, Rest of World
- Disease subtype: nodal MZL, extranodal MZL - MALT, splenic MZL
- Number of prior systemic therapy regimens: < 3,  $\geq$  3
- Bone marrow involvement at baseline: yes, no, unknown

- ECOG performance status: 0, 1, 2
- Relapsed/refractory status to the most recent prior therapy: relapsed, refractory, unknown

Subgroups may be further divided or combined based on emerging data. The ORR as determined by IRC and its 95% exact binomial CIs will be provided for participants for each subgroup. A forest plot will be created to summarize the variability in ORRs as determined by IRC for participants across subgroups.

## **7.4. Analysis of the Secondary Efficacy Parameters**

### **7.4.1. Duration of Response**

Duration of response is defined as the time from first documented evidence of CR or PR until disease progression or death due to any cause among participants who achieve an objective response (ie, CR or PR), as determined by revised response criteria for lymphomas ([Cheson et al 2014](#)). For responses assessed by IRC, the date of initial response and date of disease progression will be provided by the clinical reviewer for participants who have achieved best response of CR or PR. Censoring of DOR will follow the same algorithm as the censoring of PFS (Section 7.4.3).

The total number of responders as determined by IRC, the number of participants whose disease progressed as determined by IRC or who died, and the number of participants censored will be summarized. The Kaplan-Meier estimate of median DOR as determined by IRC and its 95% CIs will be provided, with the CIs calculated using the generalization of Brookmeyer and Crowley's method ([1982](#)) with log-log transformation ([Klein and Moeschberger 1997](#)).

A sensitivity analysis of DOR will be performed where response assessments after the time of crossover will be excluded from the determination of DOR for participants who switched to the selected treatment regimen after starting the maintenance dose. Crossover participants who have not progressed at the time of crossover will be censored at the last valid radiologic assessment on/before the time of crossover. Participants who failed to achieve a response of CR or PR on/before the time of crossover will not be considered as responders for this analysis.

The analyses described above will be summarized for all participants and participants who have at least 2 prior therapies in the FAS.

